### **Trial Design**

Triple-blinded parallel group randomized superiority controlled trial with follow-up at 1,2, 3, 6 and 12 months. 25 patients are included in each of the 2 groups. If people are included and receive treatment from the doctor, but do not show up for the first follow-up after 1 month, they will be replaced. Patients leaving the trial after 1 month of follow-up will not be replaced.

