### Randomization method

Randomization must be preceded by informed consent and power of attorney. The randomization of patients is done by an independent project secretary who is not involved in the patient treatment. This is done by a computer randomization program. Patients will be divided equally into 2 groups. The independent project secretary is then in charge of filling out randomization sheets and mixing injection for the investigator. The project secretary must prepare the 2 injections according to the description below, and must keep the randomization sheet for patients secretly and securely locked until the end of the trial, which is defined as 12 months of follow-up of patient number 50. The project secretary will also be responsible for accounting for used medicine. The project secretary has no treatment contact with the patients.

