### Blinding

**Randomization** is performed by an independent office employee not involved in patient care ([name]) using a computer generated randomization schedule (MINIMPY, Maghaei 2010) using permuted block sizes (four to six). The employee is blinded to the block sizes. The allocation of each patient is stored in a computer drive with exclusive access only for the responsible office employee ([name]).

All patients are given consecutive research numbers.

**Patients are blinded** to treatment: The syringe are blinded with tape only showing the patients research number. The content is visually identical and with similar viscosity by mixing intralipid to the placebo injection. There is a risk that blinding will be affected by the known side effects of injection with corticosteroids (flare-up and flushing). Therefore, at the first check-up after the injection, patients are asked which of the two groups they think they have been in.

**Doctors performing the injections are blinded** (JR, CB): The syringe are blinded with tape only showing the patients research number. The content is visually identical and with similar viscosity by mixing intralipid to the placebo injection.

**Data entry investigator are blinded** (JR). All data is transferred from Redcap / CRF to Xcel sheet without knowledge of treatment group allocation. After all data is transferred, the patients are divided into two groups “A” and “B” but still blinded to actual treatment groups, by information from the independent office employe.

**Statistician is blinded** (PSM): After data entry and the patients are divided in two groups: group A and group B still blinded to the actual treatment group, all statistics are performed until agreement of the results. Thereafter the blinding is broken.

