## **5 OUTCOME MEASURES**

### **Primary outcome measures:**

**The primary endpoint:** VISA-A (total and pain subscales) at 6 months. Collected by blinded evaluator via "Redcap".

All patients are thoroughly instructed in visa-A score, on all visits, as it can be difficult to understand. However, it is important that they fill out the score at home directly in the assessment-app: "Redcap" without interference of any involved investigators. Intention to treat analysis is performed by using mixed effect analysis.

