## 6 SAMPLE SIZE AND POWER

The risk of finding a difference between groups, even if there really is none, is set at 5% (risk of type I error), while the risk of overlooking a difference between the groups that is actually present is set at 20% (type II error). Individual changes from baseline over time will be calculated and all outcome parameters analyzed using mixed effect analysis. Q-Q plots will be visually examined prior to analysis to ensure that the assumption of normal distribution is not violated. Significance level is set to 0.05.

The minimum relevant difference in VISA-A is set at 15. Based on other studies on pain intensity, we expect a baseline mean of 50. Standard deviation is estimated to be 16 on VISA-A. Power of 80% provides a sample size of 20 participants in each group. We will include 25 patients in each group in case of data loss and no-shows, thereby including a total of 50 patients.

The primary analysis will be blinded and follow the intention-to-treat principle with baseline values as covariates. but we will also perform a per-protocol analysis only including patients performing at least 75% of the training programs and receive the per-protocol injections. No interim analyses will be made.

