### **Data processing:**

Entry data is registered in Redcap, where all information from each individual subject is collected.

Each patient is assigned an anonymous unidentifiable project number: AE2019-n.

Project numbers are listed on all CRF and patient diaries.

Folders, CRF and patient diaries are stored blinded only with study numbers in the departments computers. After 12 months follow-up of the last patient, a blinded statistician will make the statistical calculations. After data entry, the patients are divided in two groups: group A and group B by help from independent office employee. The primary investigator will group the patients in the two groups still blinded to the treatment group. All statistics are performed until agreement of the results. Thereafter the blinding is broken.

Analysis of data will take place in consultation with the statistician.

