### 4.2 Statistical Analysis Plan

Statistical analysis will be undertaken using PRISM version 9.3.1. All analyses will be conducted on an intention-to-treat principle using all randomised participants in the groups they were originally randomised to. A blinded statistician will perform the data analysis. In the per-protocol analysis only patients complying with the treatment protocol are included in the statistics, this means that the patient has received all per-protocol injections and performed at least 75% of the training program.

A blinded statistician will perform the data analysis.

Demographic and anthropometric characteristics (gender, age, mass, height, body mass index, sporting activities and pain duration) will be determined at the baseline visit for each treatment group.

Statistical analyses will be conducted on 1, 2, 3, 6, 9 and 12 months on all outcome measures. However, the primary end-point will be total score and subscores of the VISA-A questionnaire at 6 months.

Between-group comparisons of treatment effect for all primary and secondary outcomes, will be performed with a mixed effect analysis. To assess for superiority, mean between-group differences in changes from baseline and two-sided 95% confidence intervals will be calculated.

The ordinal scaled data of patients overall assessment of the treatment effect (Lickert score -5 to +5) will be analyzed with mixed effect analysis, if the data is found normally distributed.

The ordinal scaled data of grading the flow within the tendon into 4 categories will be calculated using non parametric statistics: Mann-Whitney U-tests.

Return to sport in percent of earlier sports activity will be compared using unpaired t-test if the data is normally distributed, otherwise non parametric analysis (Mann-Whitney) is performed.

A two-sided P value of less than 0.05 will be considered to indicate statistical significance.

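### Replacing randomised and injected patients who miss the 1-month visit, within a total of 50, conflicts with analysing all randomised participants

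*SAP*

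**What the plan says.** **Replacement.** Trial Design (section 4, Study Methods) covers people who are included and treated, "but do not show up for the first follow-up after 1 month, they will be replaced". Those who leave after the 1-month follow-up are not replaced.

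**Order of events.** Under Randomization method, allocation is made first: "The independent project secretary is then in charge of filling out randomization sheets and mixing injection for the investigator". A patient who has had an injection has therefore been randomised.

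**Size.** Trial Design gives 25 per group. Section 6 says: "We will include 25 patients in each group in case of data loss and no-shows, thereby including a total of 50 patients".

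**Analysis set.** Section 4.2 says: "All analyses will be conducted on an intention-to-treat principle using all randomised participants in the groups they were originally randomised to". Section 6 also makes the primary analysis intention-to-treat, with baseline values as covariates.

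**End of trial.** Randomization method keeps the allocation list locked until the end of the trial, "which is defined as 12 months of follow-up of patient number 50". Blinding adds: "All patients are given consecutive research numbers". Data processing uses a different marker: "After 12 months follow-up of the last patient, a blinded statistician will make the statistical calculations".

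The SAP does not say whether a replaced patient stays in the analysis, whether the newcomer gets a fresh allocation or the replaced patient's arm, or how either counts towards 50.

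**The concern.** The replacement rule is triggered by something that happens after both randomisation and injection. In ordinary use, to replace a patient within a set total means that the newcomer takes that patient's place, so the first patient drops out of the count and presumably out of the analysis. The analysed groups would then be selected on a post-treatment event, and the comparison would no longer be fully protected by randomisation.

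The Blinding section itself names flare-up and flushing as known effects of corticosteroid injection. A link between arm and early non-attendance therefore cannot be ruled out, although nothing in the SAP shows that one exists.

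At stake is the analysis set for the primary endpoint, VISA-A at 6 months. It can be read in two ways, and the SAP should settle which one applies before any analysis.

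**Working it through.** **1. The plan's own sample size.** Inputs from section 6: difference 15, SD 16, power 80%. Section 4.2 gives two-sided 0.05.

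- Normal approximation: n = 2 × (1.960 + 0.842)² × 16² / 15² = 17.9, so 18 per group.
- Two-sample t-test: 18.9, so 19 per group.

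The stated 20 is within two patients of both and is not in dispute. Going from 20 to 25 equals a 20% loss allowance, since 20 / (1 − 0.20) = 25; the SAP implies this percentage but does not state it.

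**2. Can the statements all hold?** With r replaced patients, 50 + r are randomised. The number of replacements is not in the SAP, so r below is an assumed range.

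| r replaced | Randomised (50 + r) | Share left out if the total is held at 50, r/(50 + r) |
|---|---|---|
| 0 | 50 | 0% |
| 1 | 51 | 2.0% |
| 3 | 53 | 5.7% |
| 5 | 55 | 9.1% |
| 10 | 60 | 16.7% |

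Only r = 0 satisfies both a total of 50 and an analysis of everyone randomised.

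**3. Is replacement needed for power?** For difference 15, SD 16 and a two-sided t-test at 0.05:

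| Per group | Power |
|---|---|
| 25 | 90.1% |
| 20 | 82.4% |
| 19 | 80.3% |

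Losing 5 of 25 in each arm still leaves more than 80%. Section 6 already enlarges the groups for no-shows, the same loss that the replacement rule addresses.

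**4. How far could dropping patients move the result?** With 25 retained and d dropped in an arm, and a gap g between the mean of the retained and the mean of the dropped, the arm mean shifts by d/(25 + d) × g. The SAP gives neither d nor g. Taking g as 10 to 20 VISA-A points, for illustration only:

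- One arm, 2 of 27 dropped (7.4%): 2/27 × 10 = 0.7; 2/27 × 20 = 1.5.
- One arm, 5 of 30 dropped (16.7%): 5/30 × 10 = 1.7; 5/30 × 20 = 3.3.
- 5 of 30 in one arm and 2 of 27 in the other, same gap: (5/30 − 2/27) × 10 = 0.9; × 20 = 1.9.
- Equal loss of similar patients in both arms: 0.

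**5. End-of-trial marker.** If replaced patients keep their consecutive numbers, patient 50 may not be the last patient recruited. Randomization method would then end the locked period before the point at which Data processing starts the analysis.

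**The case against.** The strongest reply is that the rule is only a recruitment instruction. Section 4.2 alone defines the analysis set, and it says all randomised participants; no sentence removes a replaced patient. On this reading, 25 per group is a target and the randomised total simply rises above 50. That reading is available, but it gives up the stated total, and the SAP does not choose it.

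A second reply is that a no-show with no post-baseline VISA-A contributes essentially nothing to a baseline-adjusted analysis of change, whether called replaced or retained. The loss is then ordinary missing data, and the rule adds bias only where follow-up was obtained, or could have been, and is discarded. This stands. It is why deleting the rule is not enough and why continued collection matters: patients are to "fill out the score at home directly in the assessment-app", so a missed clinic visit need not mean a missing primary outcome.

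Third, the shifts in step 4 rest on assumed losses and gaps. The largest needs all the loss in one arm and a 20-point gap, in a trial that blinds patients and injectors. This also stands; the figures show scale and are not evidence of bias.

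Finally, the end-of-trial point is minor. Blinding and Data processing both break the blind only after the results are agreed, so it is a mismatch of wording and not a demonstrated unblinding.

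**Conclusion.** The concern holds. As soon as one patient is replaced, the replacement rule, the total of 50 and the analysis of all randomised participants cannot all be true. This follows from the SAP's own statements and needs no assumption beyond the order of randomisation and injection that the SAP describes. That replaced patients leave the analysis is the natural reading, but it is an inference.

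The size and direction of any bias cannot be derived from the document. Under the assumed ranges, the shift runs from zero to 3.3 points against a target difference of 15. That is modest, but avoidable, and replacement is not needed to protect power. The SAP should be corrected before analysis; the point does not put the design as a whole in doubt.

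**What to change.** Either delete the replacement rule, or state that additional patients are new randomisations in the ordinary sequence and that the total may exceed 50. In either case:

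1. State that every randomised patient stays in the intention-to-treat set in the allocated arm. Recruitment had started when the SAP was signed (section 4.4), so this must also cover anyone already replaced.
2. Continue to collect the home Redcap VISA-A from patients who miss month 1.
3. Report month-1 non-attenders by arm.
4. Define the end of trial under Randomization method as 12-month follow-up of the last randomised patient, in line with Data processing.

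The cost is a few sentences in the SAP; if the protocol carries the same rule, it would need to match. Added follow-up work should be small because VISA-A is already completed at home. However, the SAP relies on instruction at visits because the score can be hard to understand, so some of these patients may still give incomplete data. If the rule is deleted, the allowance from 20 to 25 per group still covers a 20% loss. If extra patients are randomised instead, arm sizes may differ by a few.

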## **5 OUTCOME MEASURES**

### **Primary outcome measures:**

**The primary endpoint:** VISA-A (total and pain subscales) at 6 months. Collected by blinded evaluator via "Redcap".

All patients are thoroughly instructed in visa-A score, on all visits, as it can be difficult to understand. However, it is important that they fill out the score at home directly in the assessment-app: "Redcap" without interference of any involved investigators. Intention to treat analysis is performed by using mixed effect analysis.

### **Secondary outcome measures**

Lickert scale at 1, 2, 3, 6, 9 and 12 months: 11 point box scale from -5 to +5, where 0 is the status at entry, +5 is cured, and -5 is much worse.

VISA-A scores (total and pain subscales) at 1, 2, 3, 9 and 12 months.

Thickness of the Achilles tendon measured by ultrasound scan, cross-sectionel image on the thickest of the tendon at 1, 2, 3, 6, 9 and 12 months. The thickness of the "healthy" tendon is also measured for comparison.

Ultrasound Scanning Doppler Activity assessed with Color Doppler at 1, 2, 3, 6, 9 and 12 months.

After 6, 9 and 12 months, it is also assessed how many percentage of previous activity level (from before the injury) they have recovered. The patient himself states this as a percentage.

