#### **4.4 Timing of analyses**

When this statistical analysis plan was signed, recruitment to the trial had started, but analysis had not been initiated.

Statistical Analysis Plan  
Exercise/Injections in Achilles entesopathy

	Enrolment	Allocation	Month 1	Month 2	Month 3	Month 6	Month 9	Month 12
TIMEPOINT**	June 2021 – end June 2023	June 2021 – end June 2023					March 2022 end 2024	June 2022 end 2024
ENROLMENT:								
Eligibility screen	X	X						
Informed consent		X						
Allocation		X						
INTERVENTIONS:								
Intervention group			◆	◆	◆	◆		
Control group			◆	◆	◆	◆		
ASSESSMENTS:								
Diagnosis		X						
VISA-A		X	X	X	X	X	X	X
Morning pain [VAS]		X	X	X	X	X	X	X
Pain after activity [VAS]		X	X	X	X	X	X	X
Return to usual sports participation						X	X	X
Satisfaction with result of treatment			X	X	X	X	X	X
Patient diary for reporting compliance and adverse events			◆	◆	◆			
Ultrasound examinations		X	X	X	X	X	X	X
Demographics		X						

Table 1: SPIRIT figure. Schedule of enrolment, interventions and assessments

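### Return to activity is collected only at months 6, 9 and 12, so the SAP's blanket change-from-baseline and month 1–3 rules cannot apply to it, and its own named test uses no baseline information

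*SAP*

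**What the plan says.** Section 5 (Secondary outcome measures) defines the outcome and its timing: "After 6, 9 and 12 months, it is also assessed how many percentage of previous activity level (from before the injury) they have recovered". It adds: "The patient himself states this as a percentage". In Table 1 (section 4.4) the row "Return to usual sports participation" carries three marks, which fit months 6, 9 and 12. There is none at enrolment, at allocation or at months 1 to 3.

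The general rules are written for every outcome:

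- Section 6: "Individual changes from baseline over time will be calculated and all outcome parameters analyzed using mixed effect analysis".
- Section 4.2, on timing: "Statistical analyses will be conducted on 1, 2, 3, 6, 9 and 12 months on all outcome measures".
- Section 4.2, on the model: "Between-group comparisons of treatment effect for all primary and secondary outcomes, will be performed with a mixed effect analysis".
- Section 4.2, on the effect measure: "mean between-group differences in changes from baseline and two-sided 95% confidence intervals will be calculated".

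Further down, section 4.2 gives return to sport its own rule: an unpaired t-test if the data are normally distributed, otherwise Mann-Whitney. It does not say that this rule replaces the general ones. On baseline data, section 4.2 lists, among other characteristics, "sporting activities and pain duration) will be determined at the baseline visit". The form of the sporting-activity record is not given, and it has no role in the comparison. Section 6 does plan baseline values as covariates for the primary analysis.

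**The concern.** One secondary outcome falls under two incompatible rules. The general one needs an entry value and values at months 1, 2 and 3, none of which is scheduled. The specific one needs neither. The SAP does not say which governs. The choice should be settled before the groups labelled A and B are compared.

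The specific test has a weakness of its own. It compares raw follow-up percentages and uses nothing measured at entry. The inclusion criteria require at least three months of pain but no loss of activity, so patients may enter at different fractions of their former level. In groups of about 25, chance differences at entry add noise that a baseline covariate could partly remove.

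Interpretation is also at stake. Section 5 words the item as the share regained; section 4.2 treats it as a percentage of earlier sporting level. On the second reading, a hypothetical patient at 80% at entry and still at 80% at month 6 scores 80 without having gained anything. With no entry value, such a patient cannot be told apart from one who regained that level.

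**Working it through.** **The plan's own figure.** The SAP gives no sample size, SD or expected difference for return to activity. Its only such figure is for VISA-A (section 6): difference 15, SD 16, two-sided 5%, power 80%, 20 per group. The normal formula gives n = 2 × (1.96 + 0.84)² × (16/15)² = 2 × 7.84 × 1.138 = 17.8, so 18 per group; the t-test version gives 18.87, so 19. The stated 20 is reproduced to within two patients and is not touched by this point.

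**Rules against data.**

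- Analysis times set for all outcomes: months 1, 2, 3, 6, 9 and 12, six in total. Times with data for this outcome: 6, 9 and 12. Three of six have none.
- Change from baseline is the follow-up value minus the entry value. No entry percentage is scheduled, so it cannot be formed at any visit.
- The t-test or Mann-Whitney test compares group A with group B on the follow-up percentage. It can be computed at months 6, 9 and 12.
- Randomisation makes the expected difference in entry level between the groups zero, so this comparison is unbiased in expectation.

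**Precision.** Inputs: 25 per group (section 6). The SD of the percentage (20 to 30 points) and the correlation r between a baseline covariate and the outcome (0.3 to 0.6) are assumptions, because the SAP gives neither.

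Unadjusted standard error of the difference = SD × √(2/25):

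- SD 20: 5.66, so the 95% half-width is 1.96 × 5.66 = 11.1 points.
- SD 30: 8.49, so the 95% half-width is 1.96 × 8.49 = 16.6 points.

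Adjustment multiplies the variance by 1 − r² and the half-width by √(1 − r²):

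| r | Variance factor | Variance reduction | Half-width at SD 30 |
|---|---|---|---|
| none | 1.00 | – | 16.6 |
| 0.3 | 0.91 | 9% | 15.9 |
| 0.5 | 0.75 | 25% | 14.4 |
| 0.6 | 0.64 | 36% | 13.3 |

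**How far an entry imbalance carries over.** If the entry level has the same SD as the outcome, 95% of chance imbalances between two groups of 25 lie within ±11.1 points (SD 20) or ±16.6 points (SD 30). With equal SDs, a fraction r of an imbalance reaches follow-up. An imbalance of 16.6 points would therefore shift the comparison by 0.3 × 16.6 = 5.0 to 0.6 × 16.6 = 10.0 points. The unadjusted standard error already includes this variation.

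**The case against.** The strongest reply is that a specific rule ordinarily overrides a general one. On that reading the t-test or Mann-Whitney test is the plan for this outcome, it needs no entry value, and only a blanket sentence lacks an exception. This largely stands. A reader might infer from the general rules that the outcome cannot be analysed at all; the specific rule shows that it can.

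The absence of data at months 1 to 3 is also consistent within the SAP. Section 5 and Table 1 agree on months 6, 9 and 12, and the load-reduction section bars running and jumping for the first three months, so a return-to-sport percentage would mean little then. The fault is in the analysis sentence, not in data collection.

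A reader might also infer that an imbalance at entry biases the result or passes through in full. It does neither: randomisation removes bias in expectation, carry-over is only in proportion to r, and no problem with type I error or interval coverage is shown.

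Nor does the SAP state that activity never lost is scored as recovered. That is one reading of ambiguous wording. For running and jumping it is weakened further, because every patient is asked to stop and then return gradually.

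Finally, the size rests on assumed SDs and correlations, and baseline VISA-A is only a proxy for activity at entry. That is right, and it places the likely gain near the low end.

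What survives is the unreconciled wording, the unused baseline information, and the limit on reading the percentage as recovery since entry.

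**Conclusion.** The point holds as a minor one. The change-from-baseline and month 1–3 statements cannot be carried out for return to activity, and they conflict with the test that section 4.2 names for it. That test is valid but makes no use of baseline data, and its result describes level at follow-up, not gain since entry.

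The benefit of adjustment is precision only: a variance reduction of 9% to 36% for an assumed r of 0.3 to 0.6, with the low end more plausible. At an assumed SD of 30 and r of 0.3, the half-width moves only from 16.6 to 15.9 points. If the covariate turned out unrelated to the outcome, the price with 50 patients would be one residual degree of freedom (47 instead of 48). The documents do not support the stronger conclusions that the outcome is unanalysable or that its comparison is biased. The primary endpoint and the sample size are unaffected.

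**What to change.** In section 4.2, with a matching qualifier in section 6:

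1. State that return to activity is exempt from the change-from-baseline, month 1–3 and general mixed-effect statements, and is compared at months 6, 9 and 12 only.
2. Replace the unadjusted test by a comparison at each of those visits adjusted for baseline VISA-A. Add the baseline sporting-activity record as a covariate only if its form is usable, and decide this before the A/B comparison. Give the adjusted difference with its 95% confidence interval.
3. Replace the Mann-Whitney fallback by a rank-based adjusted analysis, to be used if the residuals are clearly non-normal.
4. Describe the result as current level in percent of the pre-injury level, not as recovery since entry.
5. Optionally, ask the same percentage at entry of patients not yet enrolled. The SAP is dated September 2022 and Table 1 shows enrolment to the end of June 2023. Report the answers by group for description only, since earlier patients lack them.

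The cost is a few sentences in the SAP and a covariate that is already collected. The statistician should confirm that the software named in section 4.2 can fit the adjusted and rank-based analyses. The optional step adds one question to the baseline Redcap form.
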